	Palivizumab may interfere with immunological-based RSV diagnostic tests such as some antigen detection-based assays. In addition, Palivizumab inhibits virus replication in cell culture, and therefore may also interfere with viral culture assays. Palivizumab does not interfere with reverse transcriptase-polymerase chain reaction-based assays. Assay interference could lead to falsenegative RSV diagnostic test results. Therefore, diagnostic test results, when obtained, should be used in conjunction with clinical findings to guide medical decisions	Discharge from quarantine will utilise a PCR based test instead of an antigen test.  PCR based tests will be used to confirm the incidence of infection and to quantify virus shed by infected participants.  Implications for culture-based quantification of RSV will be assessed.	
	Study procedures		
	Pain or bruising at the site where blood is drawn.	Blood samples will be obtained by a trained professional.	
	Syncope (fainting) can occur following or even before any blood draw as a psychogenic response to the needle insertion.	Blood samples will be obtained by a trained professional and procedures will be put in place to avoid injury from fainting.	
Blood Sampling	There is a possibility that in the process of collecting blood a nerve may be injured.	Procedure to be performed by qualified personnel.	
	Blood tests performed to address the health of the participants at screening and during the study may indicate that a participant has an infection that he/she was not previously aware of (such as HIV or hepatitis) or an unexpected illness.	The hVIVO doctor will provide the participant's general practitioner (GP), or doctor with a referral letter if the participant agrees.	
Nasal sampling	Collection of nasal wash samples or nasopharyngeal swabs may cause discomfort, sneezing, watery eyes, irritated nose or nose bleeding.	Sample collection will be performed by appropriately qualified and trained study staff to minimise the discomfort.	

Potential Risk of Clinical Significance	Rationale for Risk	Mitigation Strategy
	RSV infection from inoc	ulation

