# Assessment n may be on the morning or evening of any given day.

\* n+1, n+2 and n+3 are the scheduled assessments following assessment n and independent of study day. For example, Assessment n could be Day 2 evening and Assessment n+3 could be Day 4 morning.

- One positive detection by viral load qPCR assay, specific for the challenge virus, in which an aliquot of the same sample has also tested positive in a viral culture assay appropriate for detecting the challenge virus (i.e. cell-based infectivity assay) from Day +2 until discharge.

For qPCR and the cell-based infectivity assay, a positive detection is any positive numeric or ‘Detected’ value. A quantifiable detection value is any numeric value and will exclude ‘Detected’ and ‘Not detected’ values.

Viral shedding (variant 2)

One or both of the following definitions must be met:

- At least 2 positive detectable assessments by viral load qPCR assay specific for the challenge virus, reported within 4 consecutive scheduled assessments and from 2 independent samples from Day +2 until discharge
- One positive detection by viral load qPCR assay, specific for the challenge virus, in which an aliquot of the same sample has also tested positive in a viral culture assay appropriate for detecting the challenge virus (i.e. cell-based infectivity assay) from Day +2 until discharge.

Laboratory-confirmed virus-like-illness (variant 1)

Virus-like-illness (variant 1) is defined as the occurrence of laboratory-confirmed infection AND any of the following:

- Upper respiratory tract illness (defined below)

 Venn Life Sciences <small>Think Research</small>	Document Number or Project Identification: VH0001 / MB05-P-01-20
	Document Version: v3
Statistical Analysis Plan	

- Lower respiratory tract illness (defined below)
- Systemic illness (defined below)
- Febrile illness (defined below).

Laboratory-confirmed virus-like-illness (variant 2)

Virus-like-illness (variant 2) is defined as the occurrence of laboratory-confirmed infection AND symptoms of either of the following:

- any two different self-reported diary card symptoms ( $\geq$  Grade 1), or
- at least one Grade 2 self-reported symptom from one or more respiratory categories (URTI and LRTI symptoms defined below).

Laboratory-confirmed virus-like-illness (variant 3)

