### 5.2.3.2 Analysis rules

Analysis	Associated Units	Assay LLOD	Assay LLOQ	Result	Reported results	Analysis value
RSV titre (qRT-PCR)	Log10 Copies/mL	NA	2.8*	Quantifiable Titre	Value	Reported value
				DETECTED	DETECTED	LLOQ/2
				NOT DETECTED	NOT DETECTED	0
				INVALID	INVALID	Missing data point
				NOT TESTED	NOT TESTED	Missing data point
RSV titre (Plaque assay)	Log10 PFU/mL		1.7	Quantifiable Titre	Value	Reported value
				>6.04	>6.04	6.04 (ULOQ)
				DETECTED	DETECTED	LLOQ/2
				NOT DETECTED	NOT DETECTED	0
				INVALID	INVALID	Missing data point
RSV antibody titre	NAb	10	156	NDA	NDA	LLOD
				>=10 and <156	<156	LLOQ/2
				Quantifiable Titre	Value	Reported value
				≥4209	≥4209	4209 (ULOQ)
				INVALID	INVALID	Missing data point
				NOT TESTED	NOT TESTED	Missing data point

\*The LLOQ is defined as a cycle threshold (Ct) value of 33.9. This equated to 2.8 Log10 copies/mL by utilisation of a target specific copy number standard curve included in each assay run of the assay validation.

NA: Not Applicable

NDA: No Detectable Antibody

PFU: Plaque Forming Units

 Venn Life Sciences <small>Think Research</small>	Document Number or Project Identification: VH0001 / MB05-P-01-20
	Document Version: v3
Statistical Analysis Plan	

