## 6 Subgroup analysis

A “Laboratory confirmed infected” subgroup will be identified and certain pre-specified analyses will also be performed. Variant 2 of viral shedding will be used for this subgroup. Analyses expected for this subgroup are identified in section 11.1.

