## 7 Sequence of analysis

### 7.1 Interim analysis

An interim analysis aiming at reassessing the sample size will be performed once at least 50% of the planned number of challenged participants have been challenged and released from the quarantine unit. This analysis will be performed by the unblinded statistician. This analysis will be solely to confirm the powering assumptions (i.e. infection rate) within the Placebo group and may allow for additional participants to be included into the study, if needed to ensure the study is not underpowered. A second interim look to the placebo infection rate may be conducted when the targeted enrolment is reached, to further consider increasing the sample-size.

Infection rate is defined as the presence of “viral shedding” measured in nasal sample as defined in section 4.2.1.4. Only the first point of the definition variant 2 will be used for the interim analysis to estimate the infection rate.

As the interim look(s) will not compare the two treatment groups on the efficacy endpoints, and as the study is exploratory and statistical testing is not its primary goal, no adjustment to the type I error rate will be made.

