### 7.2 Final analysis

A final analysis will be performed when all endpoint data (safety and efficacy) up to study end (Day 28) are available.

A data-Review meeting (including adjudication of deviations) will be done after Last subject last visit. Data that can unblind the subject will not be reviewed during the data-review (PK, ADA).

The database lock will be done in two steps:

- The first database lock will include all data except those that can unblind the subject and those with a late availability (Plaque assay, PK, ADA data)
- the second database lock will include the remaining data (Plaque assay, PK, ADA data).

Consequently, TFLs will be produced in two steps. One set after each database lock.

All available tertiary endpoints available at that time may also be analysed in this step. An integrated CSR containing all data will be written and made available to the sponsor and the Investigator.

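### The SAP's infection definition adds an undeclared viral-culture route that palivizumab may suppress, which risks tilting infection incidence towards palivizumab

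*SAP*

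**What the plan says.** **Protocol.** Table 1 (Section 2.3.1) states that "Palivizumab inhibits virus replication in cell culture, and therefore may also interfere with viral culture assays", and that RT-PCR assays are not affected. The mitigation is that "PCR based tests will be used to confirm the incidence of infection and to quantify virus shed by infected participants". It also promises to assess what this means for culture-based quantification; I found no such analysis in the SAP. The infection endpoints in Sections 3.2 and 9.6.7 each require at least two qRT-PCR positives, quantifiable in one version and detectable in the other. Section 3.2 allows similar endpoints by culture, and Section 8.20.1.1 allows qRT-PCR and/or culture for infectivity status and rate.

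**SAP.** In Section 4.2.1.4 each shedding variant has two clauses, and meeting either is enough. The first needs two qPCR positives within four consecutive scheduled assessments. The second needs one qPCR positive "in which an aliquot of the same sample has also tested positive in a viral culture assay appropriate for detecting the challenge virus". Section 8 declares a revision to the first clause of each variant and does not mention the second.

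The definition is then used in several places:
- chi-square comparisons of infection incidence (Tables 14.2.8.1 and 14.2.8.2);
- the virus-like-illness variants, derived with both shedding definitions (Tables 14.2.9 and 14.2.10);
- the infected subgroup (Section 6): "Variant 2 of viral shedding will be used for this subgroup".

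The interim differs (Section 7.1): "Only the first point of the definition variant 2 will be used for the interim analysis to estimate the infection rate". Plaque-assay data enter only at the second of two database locks, and outputs are produced after each lock (Section 7.2).

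On quantifiability, Section 4.2.1.4 says "A quantifiable detection value is any numeric value", while Section 5.2.3.2 sets the qRT-PCR LLOQ at Ct 33.9: "This equated to 2.8 Log10 copies/mL".

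**The concern.** The assay that the protocol singles out as open to interference by the study drug has become an alternative way to be counted as infected. Interference could occur only in the palivizumab arm. Two participants with the same low-level infection could therefore be classified differently: the placebo participant qualifies by culture, while the palivizumab participant's culture is suppressed and that participant is counted as uninfected.

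The study exists to estimate the size and variance of palivizumab's effect so that later biosimilar comparisons can use them (Protocol 2.2). A tilt in incidence would carry into that use. Because Section 8 is silent, a reader would take the first-clause change to be the only departure from the protocol's infection endpoint.

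**Working it through.** **1. What the clause cannot touch.** The sample size rests on qRT-PCR VL-AUC: placebo mean 20.3, SD 17.8, 70% reduction, two-sided 5%, 80% power.

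n per group = 2 × (1.960 + 0.842)² × 17.8² / (0.70 × 20.3)² = 2 × 7.85 × 316.84 / 201.92 = 24.6, so 25.

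This reproduces the plan's figure, and culture does not enter it. The primary analysis uses qRT-PCR VL-AUC in the evaluable set, and the interim uses the PCR clause only.

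**2. Who is affected.** A negative culture never removes an infection already met by PCR. Under variant 2, only participants with a qPCR detection but no second one within four assessments depend on culture. Variant 1 is more exposed. The SAP's first example row, four *Detected* results, fails its PCR clause, but one positive culture on any of those samples would make that participant infected.

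**3. Bias in incidence.** Let q be the share of an arm that would qualify by culture only, and f the share of those suppressed on palivizumab. Neither is in the documents; I take q = 2–10% and f = 50–100% as assumptions. With no true effect and PCR infection p = 73.7% in both arms (the plan's rate):

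- placebo incidence = p + q
- palivizumab incidence = p + q(1 − f)
- bias = q × f

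For 25 per arm, enumerating all binomial outcomes of the uncorrected chi-square test gives:

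| q | f | Bias (points) | Participants of 25 | Chance of p<0.05 favouring palivizumab |
|---|---|---|---|---|
| PCR clause only | – | 0 | 0 | 2.7% |
| 2% | 50% | 1 | 0.25 | 3.3% |
| 2% | 100% | 2 | 0.5 | 3.9% |
| 5% | 50% | 2.5 | 0.625 | 4.3% |
| 5% | 100% | 5 | 1.25 | 6.5% |
| 10% | 50% | 5 | 1.25 | 7.0% |
| 10% | 100% | 10 | 2.5 | 14.3% |

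The estimate moves too. Suppose palivizumab truly halves PCR infection (73.7% to 36.85%) and culture-only cases appear on placebo only. The risk ratio is then 36.85/75.7 = 0.49 at q = 2% and 36.85/83.7 = 0.44 at q = 10%, instead of 0.50.

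**4. Infected subgroup.** Suppose culture-only cases enter on placebo only, with a VL-AUC of 0.7–2 on the scale of 20.3 (assumed), and that the arms otherwise have equal VL-AUC. The placebo subgroup mean is (0.737 × 20.3 + q × AUC) / (0.737 + q).

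- q = 2%, AUC 2: 19.82; palivizumab/placebo ratio 20.3/19.82 = 1.02
- q = 10%, AUC 0.7: 17.96; ratio 20.3/17.96 = 1.13

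The true ratio is 1.00, so the shift is against palivizumab. Cases with AUC closer to the mean would shift it less.

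**5. Quantifiable values.** Entries certain to be at or above 2.8 in the six *Yes* example rows number 0, 1, 1, 1, 1 and 0. No row guarantees the two that variant 1 needs, if quantifiable means at or above the LLOQ.

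**The case against.** The strongest reply is that the protocol says only that palivizumab may interfere and gives no size. Nasal drug concentrations are measured only if done (SAP 4.2.3), so nothing shows that a nasal aliquot would carry enough antibody to suppress culture. The clause can only add infections, and each added one still has a PCR detection. The protocol leaves room for culture in Sections 3.2 and 8.20.1.1. The affected outputs are secondary, in an exploratory study. The interim's choice of variant 2 was made to match the sample-size assumptions, not out of concern about culture.

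Much of this stands: it makes the point a risk rather than a demonstrated bias, and limits its reach. It does not remove the point. Permission for culture endpoints neither creates a combined PCR-or-culture definition nor withdraws the commitment in Table 1, and Section 8 still omits the clause.

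Four stronger readings are tempting but unsupported:
- *Incidence is biased by a known amount.* Any single figure, such as 8 points from 2 of 25 participants, is one assumed scenario.
- *The infected subgroup favours palivizumab.* For viral load, step 4 points the other way.
- *Every infection table after the first lock will be incomplete and then change.* SAP 7.2 does not say which tables follow which lock; culture-dependent tables may wait for the second.
- *The sub-LLOQ examples misclassify participants.* SAP 5.2.3.2 reports a number only for a quantifiable titre and otherwise *Detected* or *Not detected*. Read with that table, any numeric value may already mean at least 2.8.

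**Conclusion.** The point holds as a risk of differential ascertainment that the protocol itself identified and the SAP reintroduced without declaring it. It concerns infection and symptomatic-infection incidence (Objectives 6 and 7), where the direction favours palivizumab. The size is unknown: the 1–10 points and the 3.3–14.3% error rates rest wholly on the assumed q and f, with 73.7% PCR infection in both arms. With the PCR clause alone, this source of bias is zero.

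The clause also makes infected-subgroup membership depend on treatment through the assay. That subgroup is a post-randomisation selection in any case. The against-palivizumab direction rests on culture-only cases carrying little virus.

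The LLOQ mismatch is a real inconsistency between the example table and the analysis rules, but it changes results only if numeric values below 2.8 are reported.

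**What to change.** 1. In SAP 4.2.1.4 and Section 6, make the PCR clause alone the main definition for the between-arm infection and illness tables (14.2.8–14.2.10) and for the infected subgroup, as at the interim.
2. Report the PCR-or-culture definition as a labelled sensitivity analysis, with the number per arm who qualify by culture only, produced after the second database lock.
3. List the culture clause in SAP Section 8.
4. Tidy-up: state that quantifiable means at least 2.8 log10 copies/mL, and correct the six *Yes* example rows.

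The cost is SAP wording and one extra table. The downside is that participants who qualify only by culture no longer count as infected in the main analysis. Under variant 1 this includes those with repeated non-quantifiable *Detected* results plus a positive culture. The sensitivity analysis keeps them visible.

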#### 1.1.7.2. Part 2 Interventions & Duration

The total duration of study participation for a participant is up to approximately 122 days, with the following sequence and duration of study periods:

• **Screening** phase: from Day -90 to Day -4 pre-quarantine admission (Historical generic screening data collected through the hVIVO Generic Screening process may be transferred to this study after the study-specific consent form has been signed by the participant)

- **Inpatient phase:** Participants will be resident in the Quarantine Unit for approximately 16 days (from Day -3 to Day 12). Procedures will include:
  - o Pre-human viral challenge (HVC):
    - Admission to Quarantine Unit on Day -3
    - Study intervention I.V. dosing on Day -1
  - o HVC:
- Challenge Virus inoculation on Day 0
- Post-HVC
- Day 0 onwards and each day study assessments will be conducted as per Schedule of Activities
- Participants will be discharged from the Quarantine Unit on Day 12 (or may remain longer at the Principal Investigator's discretion)
- Outpatient phase: study assessments will be conducted
  - o Clinic visit for PK sample on Day 20 (±2 days)
  - Final safety follow-up visit(s): Day 28 (±3 days)

[figure not shown]

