### MB05-P-01-20 Protocol Final V2.0

+	Only the applicable Inclusion/Exclusion criteria will be reviewed at each time point.
*	All screening assessments will be performed under hVIVO Generic Screening process. Results of tests or examinations performed under hVIVO Generic Screening process, and within 90 days (90 days for viral serology and 56 days for other assessments including safety laboratory test) prior to quarantine admission may be used to determine eligibility without the need to repeat the assessment following study specific consent.
а	Height will be taken at Screening only.
b	Vital signs will be taken at the same time each day (± 1 hour).
С	Distribution of paper issues and bags will start on Day -2, with the first collection on Day -1. Thereafter collection of tissues will occur at the same timepoints (± 1 hour) with tissues distributed 24 h ahead.
d	Assessments will be performed at the same time each day during quarantine (± 1 hour). Where respiratory assessments timepoints occur together, the order of assessments will typically be 1) FOT followed by 2) PEF followed by 3) Spirometry.
е	A serum follicle stimulating hormone (FSH) test will be performed in all post-menopausal women
f	Blood serum pregnancy test (ß-HCG) will be performed in all female participants
g	Blood will be drawn under non-fasted conditions. Repeat bloods may be drawn under fasted conditions if a lipid profile (triglyceride) or glucose is required (at PI discretion).
h	Virus serology (RSV neutralisation antibody assay) will be performed to determine eligibility and seroconversion. Exploratory RSV-induced immune responses may also be assessed.
i	Nasopharyngeal swab or nasal wash for respiratory virus screen to assess for the presence of other respiratory viruses; if found positive the participant will not be eligible for the current quarantine.
j	PK blood samples are taken before the start of infusion; at end of infusion, 15mins, and 0.5, 1, 4, 8, and 12 h after infusion; and at 1, 2, 3, 7, 13, 21 and 29 days after infusion. Allowable time windows are described I section 8.19.3.
k	Post inoculation Nasal virology samples will be collected at the same time each day during quarantine (± 1 hour) and used for qRT-PCR and viral culture assay.  Optional exploratory RSV-induced immune responses may also be assessed. Nasal wash is optional under PI discretion, if NPS are being collected BD and used for viral load assessments.
I	Can be performed on Study Day -3 or Study Day -2.

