#### 4.3. Justification for Treatment Dose & Route of Administration

The dose regimen of 8mg/kg in part 1 and 8mg/kg or 15mg/kg Palivizumab in part 2 of the study is supported by data from previous clinical trials and human experience referenced in this protocol, SmPC and the accompanied document "PALIVIZUMAB Summary of relevant clinical and non-clinical data to support the use of IMP in the clinical trial".

Studies performed in adult volunteers showed that the half-life of elimination of the drug was approximately 17-20 days when administered either IV or IM and was safe through at least three-monthly injections (with the upper most test dose of 15 mg/kg). There were no safety signals in the adult volunteer studies. A single IV dose in adult volunteers at twice the recommended palivizumab prophylaxis dose has been shown to be well tolerated.

Details of clinical studies to examine the comparability of the human safety, tolerability, immunogenicity and pharmacokinetics characteristics of the liquid and the lyophilized preparations of Synagis are listed in accompanied document "PALIVIZUMAB Summary of relevant clinical and non-clinical data to support the use of IMP in the clinical trial".

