## Statistical Analysis Plan

Study Phase	Screening Phase*	QUARANTINE ISOLATION																Dis charge	Clinic visit		Early withdrawal visit	
		Admission to quarantine		Dosing	Human Viral Challenge (HVC)			Post HVC Days														
Thyroid function test	X	(X) i																				
Blood sample for serum markers (h)	X	X i		X n																X		X
Collection of respiratory samples																						
Nasopharyngeal swab / nasal wash - Respiratory pathogen screen (i)	T	X i	(X) n																			
Nasopharyngeal swab / nasal wash for Rapid viral antigen test or PCR																	X	(X) n				(X)
Nasopharyngeal swab / nasal wash Virology (k) & exploratory research	T		X					BD	BD	BD	BD	BD	BD	BD	BD	BD	BD	X				X
Safety Assessments																						
Adverse events (p)	X	←																			X	
Concomitant medications (p)	X	←																			X	

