- has any one of the following self-reported symptoms (diary card) on two consecutive scheduled assessments (from the last assessment on Day 0 to quarantine discharge (including any extended quarantine period)), at least one of which must attain grade 2 severity, or if any of the following attain grade 3 severity once:
  - Malaise
  - Headache
  - Muscles and/or joint ache
  - Chilliness / feverishness.

Febrile Illness (FI)

Febrile illness (FI) is defined as a tympanic temperature of  $\geq 37.9^{\circ}\text{C}$  occurring any time from the last assessment on Day 0 to quarantine discharge (including any extended quarantine period)).

Fold seroconversion

Seroconversion is defined as a  $\geq 4$ -fold increase in RSV specific antibodies (measured by RSV Neutralisation Assay) from baseline to follow-up post-quarantine.

Proportion (on any occasion, and on two separate occasions) of subjects with grade 2 or worse symptoms at any day and at each day post-Viral Challenge

Subjects with incomplete data and no recorded symptoms meeting the definition for these endpoints will be treated as not having met the endpoint (i.e. did not experience symptoms of grade 2 or higher).

- *Any Occasion*
  - The proportion of subjects who develop any of the 13 individual symptoms of grade 2 or higher (on any occasion, from the last assessment on Day 0 to quarantine discharge (including any extended quarantine period)) will be calculated. A single occurrence of any of these individual symptoms (of grade 2 or higher) anytime in this period corresponds to meeting the endpoint.
  - In addition, the proportion of subjects who develop any of the 13 individual symptoms of grade 2 or higher, on any occasion for each day separately, will be calculated.
- *Two Separate Occasions*
  - The proportion of subjects who develop any of the 13 individual symptoms of grade 2 or higher (on two separate occasions on any day, from the last assessment on Day 0 to quarantine discharge (including any extended quarantine period)) will be calculated. Two occurrences of any of these individual symptoms (of grade 2 or higher) in this period corresponds to meeting the endpoint.
  - In addition, the proportion of subjects who develop any of the 13 individual symptoms of grade 2 or higher, on any two occasions for each day separately, will be calculated.

 Venn Life Sciences <small>Think Research</small>	Document Number or Project Identification: VH0001 / MB05-P-01-20
	Document Version: v3

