## 5.2 Data handling conventions

### 5.2.1 Definitions

#### 5.2.1.1 Baseline

Baseline is defined as the last non-missing measurement before dosing. This will usually correspond to the measurement performed at Day-1 before first-dose, unless overruled after review of data at the DRM or otherwise stated in the appropriate endpoint section(s) below, whatever the reason for that assessment (e.g. if it is a repeat assessment, then it should be used as the baseline). However, in case of missing value at Day-1 the last available value recorded during previous visits will be used as baseline value.

If all pre-dose measurements are missing then baseline will be considered as missing, and no changes from baseline and no percentage reduction from baseline will be computed.

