##### **b) Objective 7:**

To estimate the margin and variance of prophylactic effect of IV treatment with Palivizumab administered 1 day prior to inoculation in the RSV human challenge model in healthy adults compared to Placebo [assessed by symptomatic infection in terms of incidence, duration, and peak].

Incidence of laboratory-confirmed virus-like-illness (Variant 3) will be presented. Treatment group will be compared using chi-square test on both the composite and each component (Statistical Table 14.2.9).

The following infections and illness will be summarised in one Table including data per subject and description by treatment group (Statistical Tables 14.2.10):

- “Laboratory-confirmed infection” (variant 1)
- “Laboratory-confirmed virus-like-illness” (variant 1)
- “Laboratory-confirmed virus-like-illness” (variant 2)
- Upper respiratory tract illness (URTI)
- Lower respiratory tract illness (LRTI)
- Systemic illness (SI)
- Febrile Illness (FI)
- Fold seroconversion

All Infections data will also be presented in Listing 16.2.6.5.

 Venn Life Sciences <small>Think Research</small>	Document Number or Project Identification: VH0001 / MB05-P-01-20
	Document Version: v3
Statistical Analysis Plan	

In addition, the following proportions will be tabulated per treatment group:

- Proportion of Subjects with Grade 2 or higher symptoms on any occasion at any time (Statistical Table 14.2.11.1)
- Proportion of Subjects with Grade 2 or higher Symptoms on any occasion for each day separately (Statistical Table 14.2.11.2)
- Proportion of Subjects with Grade 2 or higher Symptoms on two separate occasions at any time (Statistical Table 14.2.11.3)
- Proportion of Subjects with Grade 2 or higher Symptoms on two separate occasions for each day separately (Statistical Table 14.2.11.4)
- Proportion of Subjects with any symptom (grade  $\geq 1$ ) on any occasion at any time (Statistical Table 14.2.11.5)
- Proportion of Subjects with any symptom (grade  $\geq 1$ ) on any occasion for each day separately (Statistical Table 14.2.11.6)
- Proportion of Subjects with any symptom (grade  $\geq 1$ ) on two separate occasions at any time (Statistical Table 14.2.11.7)
- Proportion of Subjects with any symptom (grade  $\geq 1$ ) on two separate occasions for each day separately (Statistical Table 14.2.11.8)

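### Fold seroconversion is scored on a neutralisation assay while infused palivizumab is still in serum, so in the palivizumab arm only it can count drug as an immune response

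*SAP*

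**What the plan says.** SAP 4.2.1.4 lists fold seroconversion under Objective 7. It is met by a 4-fold or greater "increase in RSV specific antibodies (measured by RSV Neutralisation Assay) from baseline to follow-up post-quarantine". SAP 5.2.1.1 fixes the starting point: "Baseline is defined as the last non-missing measurement before dosing". Key note h to the Part 2 schedule (Protocol 1.3.2) names the same assay: "Virus serology (RSV neutralisation antibody assay) will be performed to determine eligibility and seroconversion". The only scheduled serology sample after quarantine is at Day 28 (±3 days), which Protocol 8.19.3 counts as 29 days after infusion.

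SAP 5.4.2.4 b) places the endpoint in Table 14.2.10: "The following infections and illness will be summarised in one Table including data per subject and description by treatment group". No test is specified for it, and SAP 8 lists it among the endpoints added to the protocol.

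On the drug, Protocol 2.1 describes palivizumab as a monoclonal antibody against RSV. Table 1 in Protocol 2.3.1 states that "Palivizumab inhibits virus replication in cell culture". Protocol 4.3 reports that the "half-life of elimination of the drug was approximately 17-20 days" in adult volunteers. Protocol 6.6 and 9.6.10 base the Part 2 dose decision on a projected exposure of at least 40 µg/mL on Day 12.

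**The concern.** A neutralisation assay measures how well serum stops the virus, whatever the source of the antibody. The baseline sample contains no palivizumab. If the Day 28 sample still contains a material amount, a rise in titre in a treated participant may be drug, immune response or both, whereas in a placebo participant it can only be immune response. The error runs in one direction and in one arm.

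At stake is a by-arm row presented among infection and illness outcomes in a study whose purpose is to estimate the size and variability of palivizumab's effect for later biosimilar work. The arm expected to have fewer infections could show more seroconversions for a reason unrelated to infection. Protocol Table 1 recognises assay interference, but its mitigation covers PCR for discharge and infection status, and an assessment of culture-based quantification. It does not mention serum serology. Neither document subtracts or blocks the drug, limits the endpoint to placebo, or notes the limitation.

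**Working it through.** The documents state no Day 28 concentration and no seroconversion rate, so there is no plan figure to reproduce.

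**Inputs**
- Concentration of 40 µg/mL on Day 12 (Protocol 6.6, 9.6.10). This is a decision minimum, not an observed mean.
- Half-life of 17 to 20 days (Protocol 4.3).
- Follow-up at 29 days after infusion, or 26 to 32 with the ±3-day window (Protocol 8.19.3).
- Titre scoring (SAP 5.2.3.2): no detectable antibody (NDA) is analysed as the LLOD, 10; a titre from 10 to below 156 as LLOQ/2 = 78; a titre from 156 upward as reported, with 4209 as the cap.

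**Step 1: drug remaining at follow-up**

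C(t) = 40 × 0.5^((t − 12) / half-life), with t in days after infusion.
- t = 29, half-life 17: 40 × 0.5^(17/17) = 20.0 µg/mL
- t = 29, half-life 20: 40 × 0.5^(17/20) = 22.2 µg/mL
- t = 32, half-life 17: 40 × 0.5^(20/17) = 17.7 µg/mL
- t = 26, half-life 20: 40 × 0.5^(14/20) = 24.6 µg/mL

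Across the window, 17.7/40 = 44% to 24.6/40 = 62% of the Day 12 level remains. If Day 12 is read on the Part 2 calendar (13 days after infusion), the figure at 29 days is 20.8 to 23.0, and 18.4 to 25.5 across the window. A participant above the minimum keeps more: an assumed 60 µg/mL at 12 days leaves 30.0 to 33.3 at 29 days.

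**Step 2: what the SAP counts as a 4-fold rise**
- Baseline NDA: the threshold is 4 × 10 = 40. Because any titre from 10 to below 156 is analysed as 78, the smallest detectable follow-up scores 78/10 = 7.8-fold and is counted.
- Baseline analysed as 78: follow-up must reach 4 × 78 = 312.
- Baseline 156: follow-up must reach 4 × 156 = 624.

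Protocol 8.19.2 requires no or low pre-existing antibody, so low baselines are expected.

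**Step 3: when drug alone is enough**

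Take the titre as a reciprocal dilution (assumption). Drug alone then gives titre = C / E, where E is the palivizumab concentration at which the assay reads its endpoint. The documents do not give E, so only break-even values can be found. At C = 20 µg/mL:
- NDA to detectable (titre 10): E ≤ 20/10 = 2 µg/mL
- Baseline analysed as 78 (titre 312): E ≤ 20/312 = 0.064 µg/mL
- Baseline 156 (titre 624): E ≤ 20/624 = 0.032 µg/mL

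These values ignore the participant's own antibody, which would add to the titre.

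**Step 4: possible effect on the table (illustration only)**

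Assume 18/25 placebo seroconversions (72%, near the 73.7% planning infection rate). A true 5/25 on palivizumab favours the drug (Fisher p = 0.0005). If drug makes all 25/25 positive, the contrast reverses (Fisher p = 0.010). The SAP plans no such test; the p-values only show how far the row could move.

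**The case against.** The strongest reply is that little depends on this row. It is one of eight items in a descriptive table. It does not enter the laboratory-confirmed infection definitions or the virus-like-illness variants (SAP 4.2.1.4), the infected subgroup (SAP 6), the interim infection rate (SAP 7.1) or the primary VL-AUC (SAP 5.4.1). The same table opens with PCR-based infection, and SAP 5.4.2.4 a) compares both infection variants by chi-square. All of this stands, and it limits the severity.

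It can also be said that 20 µg/mL is projected from a decision minimum and a historical half-life, and that serology methods sit in an Analytical Plan not available here, which may deal with drug in serum. Both points are fair. The first affects the exact level, not whether a substantial fraction of drug remains. The second leaves open a remedy at assay level, but the SAP rule as written refers to none.

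A reader might infer that the table will show palivizumab as worse, or that most treated participants will be miscounted. The documents do not support either: without a potency for this assay, the drug-caused share cannot be placed, and a baseline analysed as 78 is much harder to convert than NDA. Nor do they support inferring that the trial's conclusion on infection is compromised, because infection status rests on nasal samples, with PCR positivity required under every definition.

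**Conclusion.** The point holds at moderate severity. In the palivizumab arm the Day 28 neutralisation titre is drug plus any immune response, and the 4-fold rule can score drug as seroconversion in that arm alone. Residual drug of about 20 to 22 µg/mL (about 18 to 25 across the visit window) rests on first-order decay from 40 µg/mL at 12 days with the stated half-life. The participants most exposed to miscounting are those with an NDA baseline, for whom any detectable follow-up titre qualifies. How many treated participants would be affected cannot be computed from the documents, so the by-arm row could be distorted or reversed, and in neither case can it be read as infection.

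**What to change.** In SAP 4.2.1.4 and 5.4.2.4 b), derive and summarise fold seroconversion in the placebo arm only, as serological support for infection. For the palivizumab arm, list baseline and Day 28 titres beside the PK concentration from the same visit, which is already scheduled. Add a footnote that infused drug contributes to the titre and that a rise is not evidence of infection. Remove the palivizumab seroconversion summary from Table 14.2.10. Because PK data belong to the second database lock (SAP 7.2), this listing goes with the second set of outputs.

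If a between-arm contrast is wanted, prespecify before unblinding either a correction based on the same-visit PK concentration or an assay shown to be unaffected by palivizumab.

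The basic change costs SAP wording, one table shell and one listing, with no new samples. The descriptive by-arm seroconversion contrast is lost, but it could not be interpreted as infection. The optional contrast would cost further assay or modelling work.
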